17. SAFETY OUTCOMES

All outputs for safety outcomes will be based on the safety population.

There will be no statistical comparisons for safety data.

17.1. ADVERSE EVENTS

Both adverse events (AEs) and pre-treatment events will be coded using MedDRA central coding dictionary, Version 18.1 or higher.

The concept of “pre-treatment events” only applies to study 361-201. Pre-treatment events are untoward medical occurrences that started between 361-201 ICF and prior to the first dose of study medication in study 361-201. Adverse events of study 361-201 are untoward medical occurrences that started at the same time of or after the first dose of study medication in study 361-201, but before the first dose of extension

Document: Documentation\SAP

Author:

Version Number:

Final V1.0

Version Date:

27FEB2019

Template No: CS_TP_BS016 Revision 4
 Effective Date: 01Apr2016

Reference: CS_WI_BS005

Copyright © 2009, 2010, 2012, 2016 Quintiles Transnational Corp. All rights reserved.

The contents of this document are confidential and proprietary to Quintiles Transnational Corp. Unauthorized use, disclosure or reproduction is strictly prohibited.

study medication in study 361-202. These events will be recorded in the 361-201 database.

Adverse events of study 361-202 are untoward medical occurrences that started at the same time of or after the first dose of extension study medication in study 361-202. These events will be recorded in the 361-202 database.

If an adverse event (or pre-treatment event) of study 361-201 was ongoing as of the first dose of extension study medication, this adverse event (pre-treatment event) will be carried over to the 361-202 database and its outcome will be monitored and updated in the 361-202 database.

For the purpose of statistical analysis, only adverse events of study 361-202 that started within 9 days after the last dose of extension study medication, or had a partial or missing start date such that it cannot be determined whether the adverse event is within the 9-day window, will be included in table summaries. All 361-202 adverse events, including those that started beyond 9 days after the last dose of extension study medication, will be listed in data listings. Adverse events and pre-treatment events of study 361-201 that are carried over to the 361-202 database will be listed in data listings separately.

Whenever available, the time information should be taken into consideration when determining if a record in the AE database belongs to study 361-201 or 361-202. In the case where time isn't available, an event that started prior to the day of the first dose of extension study medication will be considered to belong to study 361-201; those that started after the day of the first dose of extension study medication will be considered to belong to study 361-202. Adverse events that started on the same day of the first dose of extension study medication will be assigned to study 361-201 or 361-202 depending on whether this AE record exists in the 361-201 database (see APPENDIX 2 for details).

See APPENDIX 2 for handling of partial dates for adverse events.

An overall summary of the incidence of adverse events within each of the categories described in the following sections will be provided as specified in the templates. This summary will also be repeated by the region, sex, age, number of prior hospitalizations for acute exacerbation of schizophrenia, and duration of schizophrenia subgroups. The overall incidence summary will also be provided for AEs related to study medication.

Listings will be provided for all AEs, AEs leading to discontinuation of study medication, AEs leading to discontinuation from the study, serious adverse events (SAE), and AEs leading to death.

For incidence summaries, each subject will be counted only once within each SOC and PT. If not otherwise specified, all summaries will present incidence (number of subjects and percentages) and number of events.

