QT	Electrocardiographic interval from the beginning of the QRS complex to the end of the T wave
QTc	QT interval corrected for heart rate
REM	Rapid eye movement
RR	Respiration rate
SAD	single ascending dose
SAE	Serious adverse event
SCID-CT	Structured Clinical Interview for DSM-IV, Clinical Trials Version
SOC	System organ class
TAAR1	trace amine associated 1 receptors
US, USA	United States, United States of America
USP	United States Pharmacopeia
VAS	Visual analogue scale
WBC	White blood cells
WHO	World Health Organization

Table 4: Definition of Key Study Terms

Terms	Definition of terms
CRF	A printed, optical, or electronic document designed to record all of the protocol required information to report to the Sponsor for each study subject.
Screened Subject	Any subject who signed the study specific informed consent and completed at least one study related procedure.
Screen Failures	Any subject who signed the study specific informed consent but either failed to meet study requirements during baseline or met study requirements at baseline but was not enrolled.
Study Drug (or Investigational Product)	Term to cover investigational drug.
Treatment Period	The period of the study in which the study drug is administered.
Enrolled Subject	Any subject who was successfully screened and was dispensed study drug.
Completed Subject	Any subject who participated throughout the duration of the study, up to and including the last follow-up visit.
Early Termination Subject	Any subject who was successfully screened and entered into the treatment period of the study, but did not complete the study.
End of Treatment	The day that the subject receives protocol-defined last dose of the study drug. This may or may not include a taper period.
End of Study	The day that the subject completes the study per the study design.

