6. STUDY ENDPOINTS

6.1. Primary Endpoints

- The incidence of overall AEs, SAEs, and AEs leading to discontinuation

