11.6.10. Visit 12E (Week 27; Day 190 ± 2, Follow-up, End of Study)

All subjects will have a follow-up prior to discharge (7 ± 2 days) after their last dose of study drug. The following procedures will be conducted during this visit:

- AE monitoring
- Prior/concomitant medications.
- Vital sign measurements (prior to ECG)

- Urine sample for β -hcG (for female subjects)
- C-SSRS
- DEQ
- PSQI

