12. SAFETY REPORTING

12.1. Definitions

12.1.1. Adverse Events

An adverse event (AE) is any untoward medical occurrence associated with the use of a drug in humans, whether or not considered drug related.

Untoward medical occurrences that occur between the time of signing the ICF and first drug administration are pre-treatment events. Those that occur after first administration of study drug are considered AEs.

An AE can, therefore, be any unfavorable and unintended sign (including an abnormal laboratory finding), symptom, or disease occurring after the administration of a medicinal (investigational) product, whether or not considered related to the medicinal (investigational) product. AEs may include the onset of new illness and the exacerbation of pre-existing conditions. AEs will be collected from after first administration of study drug to the last study visit.

The Investigator should attempt to establish a diagnosis of the event based on signs, symptoms, and/or other clinical information. In such cases, the diagnosis should be documented as the AE and not the individual signs/symptoms.

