12.4.1. Serious Adverse Event

If the Investigator or study center staff becomes aware of a SAE that occurs in a study subject after first administration of study drug through 30 days following the last dose of the study drug, this must be reported immediately to the Sponsor whether considered related or unrelated to the study drug. SAEs must be recorded on the CRF and the data recorded should agree with that on the SAE form.

Following the end of subject participation in the study, the Investigator or an authorized delegate should report SAEs “spontaneously” to PPD-PVG if considered at least possibly related to the study drug.

SAEs will be followed until resolution, loss to follow-up, stabilization of condition, or the event is otherwise explained.

In addition to the initial telephone notification, an initial SAE form as applicable must be completed and signed and sent via fax or email (see Table 1) to PPD-PVG within 24 hours of the Investigator or study center staff becoming aware of the event. The SAE form must be signed by the Investigator or appropriate designee. PPD-PVG provides the SAE form used to report SAEs.

The Sponsor or designee will promptly notify all study centers and Investigators of a SAE that is determined to be expedited to the Regulatory Authorities in accordance with applicable law(s) and regulation(s). These SAEs must be promptly reported to the Institutional Review Board

(IRB) or Independent Ethics Committee (IEC) by the Investigator or the appropriate person at the study center if required per IRB/IEC guidelines.

For the UK, the appropriate Pharmacovigilance (PVG) group must be contacted immediately upon first knowledge of the incident. The immediate report should be made by the Investigator within a very short period of time and under no circumstances should this exceed 24 hours following knowledge of the serious adverse event or pregnancy.

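### The 9-day onset limit in SAP 17.1 also governs the SAE and fatal-AE tables, so any such event captured on days 10–30 after last dose would be listed but counted in no table

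*SAP*

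**What the plan says.** SAP 17.1 limits the AE tables to "only adverse events of study 361-202 that started within 9 days after the last dose of extension study medication", together with events whose start date is too incomplete to place. All other 361-202 events are listed. SAP 17.1.4 defines the SAE table only by the seriousness field on the CRF, and SAP 17.1.5 defines the fatal-AE table only by a fatal outcome. Neither gives a window of its own, so the general limit applies. The separate table of AEs after the last extension dose also stops at day 9.

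The protocol has two collection rules. For AEs in general, section 12.1.1 states: "AEs will be collected from after first administration of study drug to the last study visit". Section 11.6.10 places that last visit: "All subjects will have a follow-up prior to discharge (7 ± 2 days) after their last dose of study drug". For SAEs, section 12.4.1 requires immediate reporting, related or not, of events occurring "after first administration of study drug through 30 days following the last dose of the study drug". It adds: "SAEs must be recorded on the CRF and the data recorded should agree with that on the SAE form". Its next paragraph says that once participation has ended, SAEs are reported spontaneously "if considered at least possibly related to the study drug".

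The primary endpoint (Protocol 6.1) is "The incidence of overall AEs, SAEs, and AEs leading to discontinuation". Protocol 15.3.6.1 limits AE summaries only from below, at the first extension dose. SAP 3.7, which lists departures from the protocol analysis, does not mention an upper limit.

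**The concern.** One onset limit is applied to two kinds of event that the protocol follows for different lengths of time. For ordinary AEs the limit costs little, because routine collection stops at about the same day. For SAEs the protocol's reporting period runs on for three more weeks. A serious event starting in those weeks, if captured, would be visible in a listing but would not contribute to the SAE incidence, and a fatal one would also be missing from the fatal-AE table.

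What is at stake is the completeness of one component of the primary endpoint. A reader who takes the SAE table as the study's SAE count would have to search the listings to find that later events exist.

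**Working it through.** **Windows side by side**

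- Latest permitted follow-up visit: 7 + 2 = 9 days after last dose (Protocol 11.6.10; Table 2, footnote c). This equals the SAP's limit.
- SAE reporting period: 30 days after last dose (Protocol 12.4.1).
- Gap: 30 − 9 = 21 days (days 10–30), or 21/30 = 70% of the post-dose SAE period.

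The limit is on onset. An AE that starts by day 9 and later proves fatal is still tabulated.

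**How certain is capture on days 10–30?** Protocol Table 4 defines a completed subject as "Any subject who participated throughout the duration of the study, up to and including the last follow-up visit". Participation thus ends at the follow-up visit, by day 9. After that, the 30-day all-SAE rule and the related-only spontaneous rule both appear to apply, and the documents do not say which governs. The CRF sentence states no time window. Capture must therefore be treated as unknown.

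**Size, by assumption.** The documents give no SAE rate. Inputs:

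- N = 180, the anticipated enrolment (Protocol 15.1; SAP 3.3).
- Table window = 26 × 7 + 9 = 191 days, assuming full exposure.
- p = SAE incidence in that window, assumed at 2%, 5% or 10%.
- a = share of day 10–30 SAEs captured, assumed at 100%, 50% or 25%.
- Constant hazard.

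Formulas:

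- h = −ln(1 − p)/191
- p30 = 1 − exp[−h(191 + 21a)]
- d = p30 − p, and added subjects = 180d
- chance of at least one added subject = 1 − (1 − d)^180

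Worked case, p = 5% and a = 1: h = −ln(0.95)/191 = 0.0002686 per day; p30 = 1 − exp(−0.0002686 × 212) = 5.534%; d = 0.534 points; 180 × 0.00534 = 0.96 subjects; 1 − (1 − 0.00534)^180 = 62%.

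| p | Added subjects, a = 100% | a = 50% | a = 25% | Chance of ≥ 1, a = 100% | a = 25% |
|---|---|---|---|---|---|
| 2% | 0.39 | 0.20 | 0.10 | 32% | 9% |
| 5% | 0.96 | 0.48 | 0.24 | 62% | 21% |
| 10% | 1.87 | 0.94 | 0.47 | 85% | 37% |

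Two assumptions are weak. Early discontinuation shortens the window, so the same p implies a higher hazard and a larger added share. The constant hazard is doubtful, because Protocol 10.5.2 has subjects referred to other continued treatment after the follow-up visit or discontinuation.

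**The case against.** The strongest defence is that the limit is deliberate, disclosed and coherent. It matches the period of active, visit-based ascertainment, and an SAE is by definition an AE, so one window for all AE tables is a reasonable basis for incidence. The SAP says openly that later events are listed, and it provides dedicated listings of SAEs and of AEs leading to death. For one or two events a listing may serve well enough. No hypothesis test, interim analysis or comparison depends on the table. All of this stands, and it is why the 9-day tables should stay.

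A reader might go further and infer that the SAP contradicts the protocol. The documents do not support that. Section 12.4.1 is a reporting rule that applies when site staff become aware of an event; nowhere does the protocol say that SAE incidence is calculated to day 30.

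A reader might also infer that every SAE on days 10–30 will be on the CRF. That does not follow either, given the related-only rule after participation ends and the absence of any statement that the CRF stays open after Visit 12E.

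On SAP 3.7, the limit can be read as putting the protocol's collection period into practice rather than changing the analysis. That is fair for general AEs. It is less so for SAEs, whose reporting period is longer, and one sentence would settle it.

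What the defence does not answer is that a listing gives no incidence, and incidence is the endpoint.

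**Conclusion.** Minor. The 9-day rule and its reach over the SAE, fatal-AE and post-last-dose tables are clear from the text, and confidence in that is high. The table templates are not in the documents, but nothing in the SAP text suggests that they override the rule. How many events are affected is uncertain. Under the stated assumptions the addition is about 0.1 to 1.9 of 180 subjects (0.05 to 1.04 percentage points), and the assumed rates and capture shares have no source in the documents. The effect is on the completeness of a descriptive primary-endpoint summary. No test or decision changes, and the events are not hidden.

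**What to change.** Keep the 9-day tables as they are.

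1. Add to SAP 17.1.4 and 17.1.5 one supplementary summary of SAEs and fatal AEs with onset through 30 days after last dose. Let AE onset date govern, not date of death, as in the existing tables.
2. Footnote it: ascertainment after the follow-up visit is passive, and the two reporting rules in Protocol 12.4.1 must be reconciled.
3. State the 9-day upper bound in SAP 3.7, because Protocol 15.3.6.1 gives only a lower bound.

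The cost is one summary, one footnote and one sentence. No new data collection is needed, because the summary would use whatever SAE records exist. The downside is that the 30-day figure is less completely ascertained and may mix two reporting rules, so it should supplement the 9-day figure and not replace it.

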10.1.1. Dosage Adjustment Criteria

All subjects will receive open-label SEP-363856 50 mg/day from Day 1 through Day 3. Beginning on Day 4, flexible dosing ranging from 25 – 75 mg/day is permitted, if deemed clinically necessary (for reasons of safety, tolerability, or efficacy) by the Investigator. On Day 4, subjects are permitted (but not required) to titrate up to 75 mg/day. Thereafter, if a dose increase is necessary to optimize efficacy it should occur at regular scheduled study visits based on Investigator judgement. Day 4 dosing changes will occur at an unscheduled visit. Thereafter, an increase in dose should occur at weekly intervals and in increments of one dose level at a time to a maximum dose of 75 mg/day. Dose reduction for tolerability purposes is allowed at any time during the study.

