17.1.2. AEs LEADING TO DISCONTINUATION OF STUDY MEDICATION

AEs leading to permanent discontinuation of study medication are AEs for which “Drug Withdrawn” is selected for “Action Taken with Study Treatment” on the AE CRF page. A summary of AEs leading to discontinuation of study medication by SOC and PT will be presented.

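### The SAP has no rule to tabulate an adverse event ongoing from 361-201 that stops treatment, becomes serious, turns fatal or worsens on extension treatment

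*SAP*

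**What the plan says.** The primary endpoint in Protocol 6.1 is "The incidence of overall AEs, SAEs, and AEs leading to discontinuation". SAP 17.1 sets what is counted towards it:

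- **Definition.** "Adverse events of study 361-202 are untoward medical occurrences that started at the same time of or after the first dose of extension study medication".
- **Entry to tables.** Summaries take "only adverse events of study 361-202 that started within 9 days after the last dose of extension study medication", plus those whose incomplete start date leaves the 9-day limit undecided.
- **Events ongoing from 361-201.** "this adverse event (pre-treatment event) will be carried over to the 361-202 database and its outcome will be monitored and updated".
- **How those are reported.** "Adverse events and pre-treatment events of study 361-201 that are carried over to the 361-202 database will be listed in data listings separately".

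Appendix 2 of the SAP assigns each record to one study or the other. It uses start and stop dates and, where the start falls on the first-dose day without a time or the dates are incomplete, whether the record already exists in the 361-201 database.

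SAP 17.1.2 to 17.1.5 then define four categories from fields on the AE form: drug withdrawn, study discontinuation, serious and fatal. For the first of these, "A summary of AEs leading to discontinuation of study medication by SOC and PT will be presented". None of these subsections mentions carried-over events.

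Protocol 12.1.1 states that "AEs may include the onset of new illness and the exacerbation of pre-existing conditions". Protocol 15.3.6.1 limits the AE summary to events occurring on or after the first extension dose.

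**The concern.** The counting rule looks at when an event began, while three of the things being counted (seriousness, discontinuation and death) can arise later in the same event. A subject may enter with an ongoing AE, continue on extension drug, and then stop because of that AE. That is an AE leading to discontinuation on extension treatment, yet the record keeps its 361-201 label and goes to a separate listing.

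Two things are at stake. The SAE and AE-discontinuation counts, both components of the primary endpoint, can be too low. The AE-discontinuation table can also show fewer subjects than the disposition table, because SAP 9 summarizes reasons for discontinuation without regard to when the AE began, and no rule reconciles the two.

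**Working it through.** The plan states no figure to reproduce here. The check is a trace through the rules, followed by a scale illustration.

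**Trace.** Take an AE that started in 361-201 and is ongoing at the first extension dose. Under Appendix 2 a known start before that dose makes it a 361-201 event, and no later change in severity, seriousness, action taken or outcome alters that.

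| What happens on extension treatment | How the documents have it recorded | Does it reach the table? |
|---|---|---|
| Turns fatal | Outcome field, which SAP 17.1 says is updated on the carried-over record | Not in the AE-death table from that record |
| Drug or study discontinuation, no worsening | No exacerbation to enter as a new AE; whether action fields are updated on the old record is not stated | Not in the AE-discontinuation table; an AE withdrawal is still counted in disposition |
| Becomes serious | Not stated; a site may enter an exacerbation as a new AE | Only if entered as new |
| Increases in severity | Not stated; a site may enter an exacerbation as a new AE | Only if entered as new |

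A permanent withdrawal attributed to a carried-over event almost certainly concerns extension drug, because Protocol 8.1 requires completion of 361-201 through Week 4.

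**Scale.** Inputs: N = 180 (Protocol 15.1, an anticipated number). The number missed, k, the number tabulated, x, and the proportion of subjects with such an event, q, are assumptions, because the documents give none of them.

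- Points lost = 100 × k/180. For k = 0, 1, 3, 5: 0, 0.56, 1.67, 2.78.
- Share of affected subjects missed = k/(x + k).
  - Table shows 5/180 (2.78%): with k = 1, 3, 5 the full count gives 3.33%, 4.44%, 5.56%, so 17%, 38%, 50% are missed.
  - Table shows 18/180 (10.0%): the full count gives 10.56%, 11.67%, 12.78%, so 5%, 14%, 22% are missed.
- Chance of at least one such subject = 1 − (1 − q)^180. For q = 0.5%, 1%, 2%, 5%: 59%, 84%, 97%, over 99.9%. The expected numbers are 0.9, 1.8, 3.6 and 9.

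A few subjects would therefore matter little to a common category and a good deal to a rare one.

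**The case against.** The strongest reply is that the two documents can be read together. Protocol 12.1.1 allows the exacerbation of a pre-existing condition to be an AE. If the site enters it as one, its onset falls on extension dosing, Appendix 2 makes it a 361-202 AE, and it is tabulated. The SAP speaks only of updating the outcome of the carried-over record, which Protocol 12.3 treats as a separate item from severity, seriousness and action taken. It is thus not established that worsening is written onto the old record. Protocol 15.3.6.1 also sets a first-dose limit of its own.

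Much of this stands, and a reader should not infer that every worsened event is lost. What it leaves open is this. The Protocol wording is permissive, and neither document tells sites to re-enter a worsened carried-over AE. The firmer instruction on worsening, in Protocol 12.1.2, covers only conditions with a hospitalization or procedure scheduled before consent. An AE that persists unchanged until the subject stops offers no exacerbation to enter. The limit in Protocol 15.3.6.1 can be read to include an exacerbation occurring on extension drug; the SAP narrows it to start date.

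Three further inferences are tempting but unsupported:

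- **That all primary components are equally affected.** Incidence counts subjects, so overall AE incidence changes only for a subject with no other extension AE. AE withdrawals remain visible in disposition.
- **That the SEP-SEP column is biased low against PBO-SEP.** Subjects from placebo can also carry events over, the imbalance cannot be derived, and SAP 17 plans no statistical comparison of safety data.
- **That the gap is tied to dose escalation.** Protocol 10.1.1 says "On Day 4, subjects are permitted (but not required) to titrate up to 75 mg/day", but the counting rule is the same at any dose.

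**Conclusion.** The concern holds as a gap in the counting rule. A carried-over AE that leads to discontinuation, becomes serious, turns fatal or worsens on extension treatment can be absent from the tables meant to count it. The gap is clearest for discontinuation without worsening, which the new-AE route does not reach, and for a fatal outcome, which the SAP directs onto the carried-over record. For worsening or new seriousness the result depends on how each site records it.

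The size is 0.56 points per missed subject on 180. The true number missed may be zero; the documents give no count of subjects entering with ongoing AEs. The events remain in the separate listing, so the defect lies in tabulation and not in data capture or in SAE reporting to the sponsor under Protocol 12.4.1.

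**What to change.** Add a paragraph to SAP 17.1:

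- Also tabulate a carried-over event if, on or after the first extension dose, it has the action Drug Withdrawn, is marked as having caused study discontinuation, becomes serious, turns fatal, or increases in severity compared with the matched 361-201 record.
- Use the date of that change as the onset date, and apply the 9-day limit to it.
- Count each episode once. If the site has entered the worsening as a new 361-202 AE, use that record and do not also flag the carried-over one; otherwise the number of events is inflated.
- Keep unchanged carried-over events in the listing only.
- Reconcile the AE-discontinuation table with AE withdrawals in disposition, and explain any difference.

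The flags are fields that SAP 17.1.2 to 17.1.5 already use, and Appendix 2 already matches records across the two databases. The cost is one paragraph and a programming flag. It needs confirmation that sites update severity, seriousness and action taken, as well as outcome, on carried-over records. Some onset dates may need a query, and reported rates may be slightly higher.
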